7.1.2.3 Reporting of Serious Adverse Events

Any SAE must be reported by the investigator if it occurs during the clinical study whether or not the event is considered to be related to the MediBeacon[®] Transdermal GFR Measurement System, or the investigational drug. All serious adverse events must be reported by the Investigator (or designee) by submitting the Serious Adverse Event Report Form (via the electronic data capture (EDC) system) or via email to MediBeacon within 24 hours of learning of the adverse event.

The Sponsor safety team, in cooperation with the Investigator, will assess all serious adverse events considered drug or device-related for potential reportability to regulatory authorities and ethical committees as an Unanticipated Adverse Device Effect (UADE) or as an expedited serious adverse event.

Note: It is also the responsibility of the Investigator to inform their Independent Ethics Committee (IEC) of other serious adverse events (i.e. non-UADEs) as required by their IEC procedures and in conformance with regulations.

SAEs must be reported within 24 hours of knowledge.

For submission of Serious Adverse Event information or Unanticipated Adverse Device Effects, the following email maybe used:

Email: [contact]

The investigator should not wait to receive additional information to document fully the event before notification to the Sponsor of an SAE, though additional information may be requested. Where applicable, information from relevant laboratory results, hospital case records, and autopsy reports should be obtained.

Instances of death, congenital abnormality, or an event that is of such clinical concern as to influence the overall assessment of safety, if brought to the attention of the investigator at any time and linked by the investigator to this study, should be reported to MediBeacon.

The sponsor or designee will promptly notify all relevant investigators and the regulatory authorities of findings that could adversely affect the safety of subjects, impact on the conduct of the study or alter the IEC approval/favorable opinion of the study. In addition, the sponsor, will expedite the reporting to all concerned investigators, to the IECs, and to the regulatory authorities of all adverse device reactions that are both serious and unanticipated.

7.1.2.4 Pregnancies

Testing for pregnancy for a female study subject with childbearing potential must be conducted at screening (or within 7 days of dosing). In addition, a urine pregnancy test will be performed prior to dosing on treatment day. Subjects who are pregnant or intend to become pregnant during the study will be excluded. Should a pregnancy occur with a study subject, the pregnancy should be reported to MediBeacon within 24 hours of the site's knowledge. All pregnancies will be followed to term, delivery or premature termination.

7.1.2.5 Device Observations / Malfunctions

All device observations, malfunctions or failures of the MediBeacon[®] Transdermal GFR Measurement System will be documented in the eCRF. In addition, failures of the sensor adhesive will be specifically documented.

7.1.2.5.1 Sensor Displacement

Prior dosing with MB-102:

Should a sensor be accidently removed (or significantly bumped) prior to administration of MB-102, it should be removed from the subject, the disposable ring removed and a new ring put on

the sensor and re-attached after re-cleaning the area with an ethanol wipe. Baseline measurements may then be re-started.

After dosing with MB-102:

If a sensor is accidently removed (or significantly bumped) following administration of MB-102 but before a tGFR is calculated, the subject will remain in the study for safety follow-ups only for the full duration required by their stratum (12 hours or 24 hours). PK sample collection and fluorescent measurements will be terminated; however, safety assessments (vital signs, ECGs and clinical safety labs) will continue to be performed.

7.1.2.6 Clinical Laboratory Evaluation

Clinical laboratory assessments (**Table 3**) will be performed by a central lab. Reference ranges will be used by the investigator to assess the laboratory data for clinical significance and changes relative to baseline measurements. Clinically significant changes in laboratory values will be documented as adverse events.

Chemistry Panel	Hematology	Other required lab tests			
 Alkaline Phosphatase Alanine Aminotransferase (ALT) Albumin Aspartate Aminotransferase (AST) Bilirubin (total and direct) Blood Urea Nitrogen (BUN) Calcium (Ca) Carbon dioxide (CO2) Chloride (C) Creatinine (SCr) Glucose Phosphorus Potassium Sodium Total Protein Uric acid BUN/Creatinine ratio 	 Hematocrit Hemoglobin WBC RBC Platelets Differentials Neutrophils Lymphocytes Monocytes Eosinophils Basophils Coagulation Parameters Only performed at screening PT INR aPTT 	 For WOCBP Serum pregnancy test (screening and a urine dipstick on day of dosing Urinalysis Protein Glucose Ketones Hemoglobin Bilirubin Urobilinogen Acetone Nitrite Leucocytes pH Specific gravity Color Bacteria If abnormalities are seen, then microscopic examination will be performed 			
COVID-19 Test at screening and prior to dosing (local testing)					

Table 3 Clinical Laboratory Analytes

7.1.2.7 Vital Signs

Vital signs (including blood pressure, pulse, respiration, and temperature) will be measured at screening, at multiple timepoints on dosing day(s), and at the follow-up visit. Vital signs should be collected while the subject is in a seated position and after resting for approximately 5 minutes for all measurements. Temperature is only collected at screening, pre-dose, and the completion of the dosing day, and at the follow-up visit.

7.1.2.8 Physical Examinations or Limited Physical Assessments

Physical examinations (when conducted by a physician, or other medically qualified investigator) or limited physical assessments (when performed by a nurse or other qualified individual) should include at a minimum an assessment of the head, ears, eyes, nose, throat (HEENT), respiratory, cardiovascular, and gastrointestinal systems. It is preferred that the same medical professional perform the baseline and post dosing assessments. Significant findings that were present prior to dosing must be included in the Medical History eCRF page. Significant new findings that begin or worsen after dosing must be recorded on the AE page of the eCRF. Clinically significant abnormalities occurring post-dose should be evaluated by a physician and noted as AEs.

The study investigator will assess the subject for the occurrence of clinically significant new findings that begin or worsen after dosing which must be recorded as an AE on the eCRF page. A full physical exam should be conducted at screening and limited physical assessments may be conducted at other time points and must also be inclusive of the relevant organ or body system of interest for assessing the AE.

7.1.2.9 ECGs

Standard 12 lead ECGs will be collected at screening, prior to dosing and at 700 minutes (± 5 min). The following parameters will be assessed: interpretation, ventricular rate, PR interval, QRS duration, QT, and QTcF.

Subjects should be allowed to rest quietly approximately 10-15 minutes prior to their ECG. Additional ECGs may be collected if an issue or safety concern is noted.

An appropriately trained and experienced investigator will interpret the ECGs. A subject with an abnormal clinically significant ECG during screening does not qualify for the study. A subject with an abnormal not clinically significant ECG does not qualify for dosing without investigator comment on the ECG source document/eCRF.

7.1.2.10 PK Sample Collection

PK samples will be collected at the timepoints noted in **Table 2.** Recommendations for venous access and sample processing information are available in the Study Procedure Manual. PK samples should be collected in a manner to prevent haemolysis and placed on ice until processed and aliquoted into cryovials. PK samples must be stored frozen at -70 to -80°C until shipped for PK analysis.

7.1.2.11 Mexameter[®] Measurements

A commercially available Mexameter[®] device will be provided to the sites for the measurement of skin pigment (melanin) and erythema. The device should be used in accordance with the instructions provided in the Study Procedure Manual (including pre-use calibration). Measurements should be performed on subjects when they are not in close proximity to a window and should be made on the approximate location of sensor placement. It is advisable, when required, to clip excess hair as early in the dosing day as possible to allow transient redness due to the clipping process to fade. The site should note any skin irritation due to clipping as medical history. Mexameter[®] measurements of melanin and erythema will be collected prior to sensor placement.

7.2 Safety Review Committee

A Safety Review Committee (SRC) will be convened and will include the medical monitor, the safety manager(s), clinical monitor(s) and clinical manager. The SRC will oversee safety data (AEs, vitals, clinical labs, ECG data, etc.) generated by enrolled study subjects on the trial. In addition, they will review all SAEs and UADEs and clinically significant safety observations noted during the study. Oversight work and study related decisions will be performed in accordance with a written Safety Review Committee Plan.

8 Information for the Investigator: Potential Risks of the Device

Adverse events that may be anticipated in this clinical study are outlined for the investigational drug and the MediBeacon[®] Transdermal GFR Measurement System.

8.1 Investigational Drug

Clinical data from the Pilot 1A and 1B studies (total n = 32 subjects) included the following adverse events:

- Pilot 1A (n = 16)
 - Vasovagal reaction (1 subject)
 - Dizziness (1 subject, 2 events)

These events occurred in fasting subjects shortly after dosing and resolved on that day. No other AEs, injection site reactions, clinically significant laboratory values or significant changes in vital signs were noted during this study.

- Pilot 1B (n = 16)
 - Headaches (56.3% of subjects)
 - Erythema (at the site of the adhesive) (100% of subjects)
 - Diarrhoea (1 subject)
 - Dizziness (occurring in 1 subject following release from the study center)

Erythema was thought to be related to the adhesive used to adhere the sensor to the skin. Headaches were deemed related to the head strap required to hold the forehead sensor in place. Sensor placement on forehead was discontinued post Pilot 1B.

MB-102 is excreted in the urine. Therefore, urine discoloration (chromaturia) is expected but has not been considered an adverse event in prior studies.

In the Pilot 2 study, a total of 234 subjects with normal to compromised renal function have been exposed to MB-102. A total of 120 subjects received a dose of 4 μ mol/kg followed by a 5 mL injection of iohexol. Seventy (70) subjects received a single dose only (no iohexol) of 4 μ mol/kg of MB-102) and 44 have received a fixed dose of 130 mg (7 mL). All reported AEs were mild or moderate in severity and resolved without sequalae. Overall, MB-102 given in conjunction with or without iohexol was well tolerated in this subject population.

A total of 40 adverse events were reported in 28 treated subjects in Groups 1, 2 and 3 for an AE rate of 12.0% in the treated population. A total of 31 events were considered mild and 9 moderate events occurred in 5 subjects (2.5% of the population). There were no severe events reported. There were no Serious Adverse Events (SAEs) reported during the study. There were no Unanticipated Adverse Device Effects (UADEs) reported during the study.

Four AEs, dyspepsia, chromaturia, hot flush and (facial) rash were considered related to investigational product (MB-102); all events resolved by study completion. Dyspepsia and chromaturia were also considered to be related to iohexol. Of note, chromaturia is an expected effect of MB-102 (noted in the Investigator's Brochure) and expected in all subjects as the excretion of MB-102 will color the urine of subjects receiving the product. It is not a documented effect of iohexol (per the label).

Seven (7) AEs occurring in 7 subjects were considered related to the device (sensor attachment); these included application site erythema, dermatitis, and pruritus and were considered related to the adhesive material used to hold the sensor in place. Two events of application site discoloration (melanin spot at the sensor location) were noted in 2 subjects in the SOG cohort which resolved within 24 hours of removal of the sensor. Other reported AEs (conjunctivitis, nausea, vomiting, cardiac murmur, headache, anxiety, micturition urgency, pollakiuria, urine odor abnormal, peripheral oedema, fatigue, and a pruritis event [not at the sensor location] were considered not related to MB-102, the sensor device or iohexol. Injection site reactions (bruising, erythema, extravasation) were also not considered related to MB-102.

A pivotal trial (protocol 100-003) enrolled 249 subjects. There were 31 adverse events reported in 26 subjects (10.4%). All reported events are mild or moderate in severity. Only 1 event (moderate nausea) was considered related to MB-102. No severe or serious events have been reported.

There may also be other risks that are unforeseen at this time. For additional information on the risk profile, please reference the current Investigator's Brochure.

8.2 MediBeacon[®] Transdermal GFR Measurement System

There are no direct risks associated with the MediBeacon[®] Transdermal GFR Measurement System (monitor portion) as it does not contact the study subject. Adverse events observed from the sensors are with regard to the methods used to affix it to the study subject. Risks may include a reaction to the sensor or adhesive material or the adhesive used on the skin clip.

8.2.1 Adhesive Clip

As with the adhesive used on the sensors, there is the chance of reaction to the adhesive used to attach the clip to the skin. Reactions could include redness, itchiness or other localized skin reactions. Clips will be provided, however other means (surgical tape, tegaderm, etc.) to secure the sensor cord may be used.

8.3 Trial Procedures

Blood collection may lead to light-headedness and dizziness in some study subjects. It is recommended to ensure subjects continue to hydrate and eat during the dosing day to mitigate the effect of blood loss.

Bruising and pain at the site of the venous catheters may also be expected.

8.3.1 Dose Extravasations

Should a dosing extravasation occur, a subject may report pain or burning during the injection. Subjects should be queried during the injection regarding any sensation. Subjects with MB-102 or saline extravasations will be discontinued from PK collection and fluorescent measurements but continued in the study for safety. All extravasations will be collected as adverse events and protocol deviations.

9 Statistical Methods

9.1 Overview

The transdermal-derived GFR data (tGFR) is obtained directly from the MediBeacon[®] Transdermal GFR Measurement System (TGFR) for each subject. This tGFR value is compared to the subject's nGFR_{BSA} for the study endpoint determination.

9.2 Analysis Populations

The following analysis populations will be defined for the study:

Intent-to-Measure (ITM) Population – The ITM population will consist of all subjects who are enrolled in the study in Stratum 1 & 2 and for whom an average session tGFR or an average snapshot tGFR* has been calculated, and who have not had any major protocol deviations that would impact TGFR system performance.

- Modified Intent-to-Measure (mITM) Population The mITM population will consist of all subjects in the ITM population with no outlier PK parameters.
- Safety Population The safety population will consist of all subjects who are enrolled in the study and have been dosed with MB-102.
- Pharmacokinetic (PK) Population The pharmacokinetic population will consist of all subjects who are enrolled in the study and have any PK data.

* Note: this includes short gaps in data that are less than 30 minutes due to a resumption of the monitoring session where an "average snapshot GFR" is reported instead of a "average session GFR".

The mITM population will be the primary analysis set for all effectiveness analyses. The Safety Population will be used for the analysis of all safety variables and baseline characteristics. The PK Population will be used for the analyses of PK data.

Note: Data from the Run-in Cohort and Validation Cohort 1 will be considered Tuning Data and will not be used in the final analyses.

9.3 Subject Disposition

The number and percentage of subjects who complete the study or who terminate early from the study and the reasons for early termination will be collected and reported. Subjects will be considered to have completed the study if they complete the dosing day.

The number and percentage of subjects in each analysis population will be presented. Percentages will be based on the number of subjects enrolled.

9.4 Plasma Pharmacokinetic Analyses

The pharmacokinetic objective is to characterize the single dose pharmacokinetics of MB-102 following IV bolus dosing, specifically, to obtain the clearance and total volume of distribution of MB-102 using compartmental methods in Phoenix WinNonlin (Certara, Version 8.1 or higher).

Based on prior data, it is expected that a two-compartment model will adequately describe the pharmacokinetic profiles of MB-102. The following two-compartmental pharmacokinetic parameters will be determined:

- \triangleright C_{max}: The maximum plasma concentration.
- > AUC: Area under the plasma concentration-time curve
- > $t_{1/2\alpha}$: Half-life associated with distribution phase
- > $t_{1/2\beta}$: Half-life associated with elimination phase
- > $t_{1/2}$: elimination half-life from central compartment.

- V: Total volume of distribution
- CL: Systemic clearance
- > V1: Volume of distribution for central compartment
- > V2: Volume of distribution for peripheral compartment

The two key PK parameters from compartmental analysis are CL and V. The clearance (CL) derived from the two-compartment model is the plasma-derived GFR used to calculate the BSA indexed nGFR that is the comparison to the tGFR for the P30 calculations. V is used in the calculation of GFR indexed to volume of distribution.

All PK concentrations and parameters will be listed. As each subject will have a unique GFR measurement, summary statistics are not applicable in this analysis.

Individual figures will be provided for plasma PK concentrations. All figures will be produced on both linear-linear and logarithmic- linear scales with data and the two-compartment fit.

9.5 Primary Endpoint Analysis

The primary endpoint is the performance measure of P30 for transdermal-derived GFR with respect to the plasma-derived indexed GFR, with a 95% confidence interval. The performance goal is 85%. Success for the study will be that the lower limit of the 95% CI is greater than 85%.

Prior data demonstrated for a P30 true value of 0.95, alpha of 0.025, performance goal of 85%, power of 90%, the one-sided exact binomial test yields a sample size of 102. As the reusable sensor is new, an adaptive trial design will be employed.

A Run-in Cohort of up to 30 evaluable subjects will be enrolled to test monitor algorithm settings with the TGFR reusable sensor with disposable adhesive ring. Additional run-in subjects may be enrolled at new clinical sites to ensure protocol compliance. Run-in subject data will be considered tuning data. The following will be enrolled into the run-in cohort:

- At least 5 subjects will be enrolled in Stratum 2
- At least 4 subjects in each of the FSS I-II; III-IV and V-VI
- Validation Cohort 1 (approximately 20 evaluable subjects) will be used to confirm final algorithm selection. Validation Cohort 1 subject data will be considered tuning data.
- Validation Cohort 2 (approximately 75 evaluable subjects) will be analysed in an interim analysis to compare results against the primary endpoint specification. At that time, the primary endpoint null hypothesis will be tested using an exact binomial test at a one-sided nominal alpha level of 0.0150 using the method of Pocock for a two-stage design with the interim analysis performed based on the first 53.57% of the planned number of subjects. At the final analysis, the primary endpoint null hypothesis will also be tested at a one-sided nominal alpha level of 0.0150. This will control the overall Type I error rate at the one-sided 0.025 level.

- If the primary endpoint has been achieved, the study will be terminated. If not, the trial will be continued.
- Validation Cohort 3 (approximately 65 evaluable subjects) will be enrolled in the event the interim analysis did not meet the primary outcome measure. Final analysis will be of the 140 evaluable subjects.

9.6 Safety Analyses

Safety of MB-102 will be evaluated through treatment emergent adverse events (TEAEs), where treatment emergence is defined with respect to the first dose of MB-102.

Safety of the MediBeacon[®] Transdermal GFR Measurement System will be evaluated through TEAEs, where treatment emergence is defined with respect to the start time of Transdermal GFR Measurement System use (placement of the sensor on the skin).

Additional safety variables include physical examinations, clinical laboratory assessments, ECGs, and concomitant medication use.

All safety analyses will be done for subjects receiving a single dose of MB-102.

9.6.1 Treatment-Emergent Adverse Events

AEs will be coded using the *Medical Dictionary for Regulatory Activities* (MedDRA). The system organ class and preferred term for each AE will be available, along with the verbatim reported term, event start and stop dates/times, seriousness, severity, relationship to treatment/device, action taken, and event outcome. SAEs will also be documented in a case narrative format.

The overall numbers and percentages of subjects who experienced any treatment-emergent AEs (TEAEs) will be presented. TEAEs will also be summarized at the subject level by system organ class and preferred term, and at the event level by system organ class/preferred term and severity and by system organ class/ preferred term and relationship to treatment.

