	7.5	Outcome o	f the Event	24
	7.6	Evaluation	of Device Malfunctions	24
8	C	GENERAL STA	TISTICAL CONSIDERATIONS	25
	8.1	Analysis Se	ts	25
	8.2	Sample Size	e Determination	25
	8.3	Pooling Da	ta Across Sites	26
	8.4	Handling o	f Missing Data	27
	8.5	Statistical S	Software	27
	8.6	Descriptive	Statistics	27
	8.7	Statistical S	Significance	27
	8.8	Subject Dis	position	27
	8.9	Analysis		28
9	(CHANGES FRO	OM PLANNED ANALYSES	28
1(0 9	SUBJECT LISTI	NGS	28
1:	1 7	TABLES		29

Statistical Analysis Plan		Page 6 of 29
MediBeacon Inc.	An Open Label, Multi-Center, Safety and Pharmacokinetic Bridging Study of MB-102 (Relmapirazin) and the Use of the MediBeacon [®] Transdermal GFR Measurement System using the TGFR Reusable Sensor with Disposable Adhesive Ring in Normal and Renal Compromised Subjects for the Evaluation of Kidney Function	Ver 4.0

1 Introduction

This statistical analysis plan (SAP) describes the planned statistical methods to be used during the reporting and analysis of data collected under the Clinical Investigation Protocol, "An Open Label, Multi-Center, Safety and Pharmacokinetic Bridging Study of MB-102 (Relmapirazin) and the Use of the MediBeacon® Transdermal GFR Measurement System using the TGFR Reusable Sensor with Disposable Adhesive Ring in Normal and Renal Compromised Subjects for the Evaluation of Kidney Function". This SAP should be read in conjunction with the study Clinical Investigation Plan and associated case report forms (CRFs). This version of the analysis plan has been developed with respect to the Study Protocol Version 5.1. Any revisions to the protocol or CRFs that impact the planned analyses may require updates to the SAP. If there are any discrepancies between the SAP and the protocol, the SAP will prevail.

2 Study Design

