Significant findings that were noted to be present at or prior to dosing must be included in the relevant medical history page of the eCRF. Significant new findings that begin or worsen after dosing must be recorded on the AE page of the eCRF. Subjects should be followed until the event is resolved or stabilized. AEs are collected from the time of initial sensor placement until the completion of the follow-up visit.

All reported TEAEs, including unanticipated adverse device effects (UADE), and serious adverse events (SAE) will be summarized for all enrolled subjects. The overall numbers and percentages of subjects who experienced any TEAEs will be presented. In addition to the TEAEs, description of all TEAEs, including description/term of the symptom event (underlying diagnosis), the date of first occurrence and date of resolution (if applicable), classification of serious or not serious, severity, causal relationship, action taken, and event outcome will be listed. TEAEs will also be summarized at the subject level by system organ class and preferred term, and at the event level by system organ class/preferred term and severity and by system organ class/ preferred term and relationship to treatment.

In addition to the events reported as AEs, the parameters of clinical laboratory tests including clinical chemistry, hematology, urinalysis and coagulation parameters will be summarized using the descriptive

Statistical Analysis Plan		Page 23 of 29
MediBeacon Inc.	An Open Label, Multi-Center, Safety and Pharmacokinetic Bridging Study of MB-102 (Relmapirazin) and the Use of the MediBeacon [®] Transdermal GFR Measurement System using the TGFR Reusable Sensor with Disposable Adhesive Ring in Normal and Renal Compromised Subjects for the Evaluation of Kidney Function	Ver 4.0

statistics. Clinical laboratory analytes are presented in **Table 1**. More information on descriptive statistics is presented in **Section 8.6**.

ECG data will be listed. Concomitant medications, coded using the World Health Organization (WHO) drug dictionary, administered within 3 days prior to MB-102 dose administration and through the follow-up study visit will be also listed. Furthermore, concomitant non-drug therapies will be listed.

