7.3 Assessment of Severity

The severity of the adverse events will be rated based upon the following grades:

- Mild: results in minimal transient impairment of a body function or damage to a body structure and/or does not require any intervention other than monitoring or OTC medication.
- Moderate: Results in moderate transient impairment of a body function or transient damage to a body structure and/or requires intervention, such as administration of medication or transfusion or

Statistical Analysis Plan		Page 24 of 29
MediBeacon Inc.	An Open Label, Multi-Center, Safety and Pharmacokinetic Bridging Study of MB-102 (Relmapirazin) and the Use of the MediBeacon [®] Transdermal GFR Measurement System using the TGFR Reusable Sensor with Disposable Adhesive Ring in Normal and Renal Compromised Subjects for the Evaluation of Kidney Function	Ver 4.0

laparoscopic or endoscopic procedure to prevent permanent impairment of a body function or damage to a body structure.

Severe: An event which is life threatening, results in permanent impairment of a body function or permanent damage to a body structure or necessitates significant intervention, such as major surgery, to prevent permanent impairment of a body function or permanent damage to a body structure. The term severe is often used to describe the intensity (severity) of a specific event (as in mild, moderate, or severe myocardial infarction); the event itself, however, may be of relatively minor medical significance (such as severe headache). This is not the same as serious, which is based on patient/event outcome or action criteria usually associated with events that pose a threat to a patient's life or functioning. Seriousness (not severity) serves as a guide for defining regulatory reporting obligations. An event that changes in severity (gets worse or gets better) should be noted as its worst severity.

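### TEAE severity and relationship are tabulated by event only, so the planned tables do not show how many subjects had a related TEAE or how subjects fall by worst severity

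*Protocol*

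**What the plan says.** Protocol 9.6.1 and SAP section 7 give the same set of TEAE summaries.

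- Two are counts of subjects. The first is the overall one: "The overall numbers and percentages of subjects who experienced any TEAEs will be presented". The second is by term: "TEAEs will also be summarized at the subject level by system organ class and preferred term". Neither is split by severity or relationship.
- Severity and relationship are summarized "at the event level by system organ class/preferred term and severity and by system organ class/ preferred term and relationship to treatment".
- SAP section 7 also plans a listing of every TEAE, in which "classification of serious or not serious, severity, causal relationship, action taken, and event outcome will be listed". Protocol 9.6.1 adds narratives for SAEs.

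The only worst-severity rule, in Protocol 7.1.2.1 and SAP 7.3, works within a single event: "An event that changes in severity (gets worse or gets better) should be noted as its worst severity". It does not say how to classify a subject who has several events. SAP section 1 settles conflicts between the documents ("If there are any discrepancies between the SAP and the protocol, the SAP will prevail"), but here the two agree, so that rule changes nothing.

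**The concern.** Adverse events cluster within people. A table of events by severity or relationship shows what share of the events was moderate or related. It does not show what share of the exposed subjects had a moderate or related event, and it has no subject denominator. Evaluating safety is one of the two objectives in Protocol section 4, and the number of subjects with at least one related event, or by worst severity, is what most readers of a safety section look for. If the tables are built as written, a reader must either count from the listing or risk taking an event share for a subject risk.

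**Working it through.** **1. What the planned outputs contain (Protocol 9.6.1, SAP section 7).**

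| Quantity | Subject count tabulated? | Event count tabulated? | In the listing? |
|---|---|---|---|
| Any TEAE | yes | not stated | yes |
| By system organ class and preferred term | yes | not stated | yes |
| By severity | no | yes | yes |
| By relationship | no | yes | yes |

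No other section of either document supplies the two missing subject counts.

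**2. Reproducing the sponsor's own subject rates (Protocol 8.1).** "In the Pilot 2 study, a total of 234 subjects with normal to compromised renal function have been exposed to MB-102". Of these, 28 had an adverse event: 28/234 = 11.97%, printed as 12.0%. In the pivotal trial 26 of 249 subjects had one: 26/249 = 10.44%, printed as 10.4%. Both figures are subjects with at least one event divided by all subjects, and the planned any-TEAE summary will produce the same quantity.

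**3. Events per affected subject (Protocol 8.1).**

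- Pilot 2, all events: 40/28 = 1.43
- Pilot 2, moderate events: 9/5 = 1.80
- Pilot 2, device-related events: 7/7 = 1.00
- Pivotal trial, all events: 31/26 = 1.19

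Events and subjects differ in three of the four. For device-related events they coincide.

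**4. The same Pilot 2 moderate events in two units.**

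- Share of events: 9/40 = 22.5%
- Share of subjects with any event: 5/28 = 17.9%
- Share of exposed subjects: 5/234 = 2.1%

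Most of the distance from 22.5% to 2.1% comes from the change of denominator, from events to exposed subjects. The effect of clustering alone is 9 against 5 in the numerator, or 22.5% against 17.9% among those affected. Either way, the event share does not estimate the subject risk.

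**5. What an event count leaves open.** Nine events alone could come from 1 to 9 subjects, that is 1/234 = 0.4% to 9/234 = 3.8% of those exposed. Once the 5 subjects are known, at least one had 2 or more events (9/5 rounded up). The most that one subject could hold is 9 − (5 − 1) = 5 of the 9, or 56%.

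**6. Scale in this study (illustration).** SAP 8.1 defines the Safety Population as all enrolled and dosed subjects. If every cohort fills as planned, with no replacements or repeat entries, a stop at the interim gives 30 + 20 + 75 = 125 subjects, and the full study gives 125 + 65 = 190. Assuming the earlier subject rates of 10.4% to 12.0% apply, the expected numbers of affected subjects are:

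- at 125: 0.104 × 125 = 13 to 0.120 × 125 = 15
- at 190: 0.104 × 190 = 20 to 0.120 × 190 = 23

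These are small enough to count from the listing by hand.

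**The case against.** The plan is explicit and consistent between the two documents, and nothing is lost from the data. The listing carries severity and causality for every TEAE, and at 13 to 23 affected subjects the missing counts take little time to derive. All of this stands, and it limits the point to presentation. A listing is still not a planned summary: it sets no denominator and no rule for a subject with several events.

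Four stronger readings are tempting, and the documents do not support them.

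- **That these counts would never be reported, or that results could not be set beside earlier studies.** The listing rules out the first. As to the second, the any-TEAE subject rate matches the 12.0% and 10.4% already reported. Protocol 8.1 also gives much of the earlier severity and relationship data by event: 31 mild events, four events related to MB-102 in Pilot 2, and one in the pivotal trial.
- **That a bridging study needs these tables to compare the reusable sensor with the earlier one.** Neither document plans a comparative safety analysis or sets a safety hypothesis or performance goal. The study is single-arm (SAP 2.5), and the objective is to evaluate safety.
- **That the tables would rest on the 75 subjects of Validation Cohort 2, where one subject with a few events would dominate.** SAP 8.1 restricts only the ITM and mITM populations to Validation Cohorts 2 and 3. Protocol 5.4.5 and SAP 2.3 put everyone exposed to MB-102 into the safety analysis. The tables are also split by term, so one subject can dominate a preferred-term row only through repeats of that term.
- **That the percentage printed in Protocol 8.1 for the 5 subjects with moderate events, 2.5% against 2.1% on 234, is part of the problem.** It is background data with no stated denominator, and nothing here depends on it.

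**Conclusion.** The point holds as a modest one. The planned tables in both documents omit the number and percentage of subjects with a related TEAE and of subjects by worst severity. The sponsor's own figures, from 1.00 to 1.80 events per affected subject, show that event counts cannot be relied on to stand in for them. The consequence is limited: the counts can be recovered from the listing, earlier events were all mild or moderate, the any-TEAE rate is unaffected, and the primary endpoint is not touched. The reading rests on the wording of Protocol 9.6.1 and SAP section 7. No layouts of safety tables appear in the documents (SAP section 11 holds only the laboratory analytes), so fuller tables may exist elsewhere. The change is a low-priority improvement that uses data already collected.

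**What to change.** In Protocol 9.6.1 and SAP section 7, add subject-level tables, overall and by system organ class and preferred term. Count each subject once at worst severity and once at strongest relationship, as n (%) of the Safety Population (all dosed subjects), and keep the event counts beside them.

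Three details need settling in the same edit:

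- **Drug and device.** Show relationship separately for each. Protocol 9.6 evaluates them separately and starts treatment emergence at different times (first dose, sensor placement).
- **Repeat participants.** Protocol 6.12 lets a person take part up to four times, with a new, cross-referenced ID on entry to Validation Cohort 2 or 3. State whether the tables count by person or by ID, for both numerator and denominator.
- **Causality scale.** Protocol 7.1.2.1 has five categories; SAP 7.2 has four and lacks Probable. Reconcile them, then state which categories count as related.

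The cost is a few sentences in each document and some extra table programming. No new data are needed, and the sample size and primary analysis do not change.
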